5.4.2 Ventilator Settings

The device is designed for use with standard adult ventilator settings. An intermittent positive pressure ventilatory mode (i.e., not constant positive airway pressure [CPAP] or t-piece) is required to activate the device to deliver aerosol during the inspiration phase. A Heat-Moisture Exchanger (HME) may be used in the device circuit.

The site will utilize OSU's Standard of Care (SOC) mechanical ventilation guidelines for care of patients for COVID-19 with ARDS. The following ventilator parameters will be assessed daily while on VentaProst: Ventilator type, Mode, FiO₂, Inspiratory Time, Mean Airway Pressure, Peak Inspiratory Pressure, Positive End Expiratory Pressure, Respiratory Rate and Tidal Volume.

5.4.3 Device Supply

All device supplies will be provided by Aerogen Pharma Limited. The serial numbers for the controllers, flow sensor, and nebulizer will also be recorded in an IP accountability dispensing log. Used and unused devices will be inventoried and returned to the Sponsor or Sponsor's designee.

5.4.4 Device Replacement

Devices may be replaced at any time if there a suspicion of malfunction, but must be replaced if:

- The investigator suspects that, due to device malfunction, less than 90% of the total dose of study medication is being delivered. Reduced doses must be estimated and recorded in the patient's medical record and source documentation.
- The investigator suspects the device is not performing optimally for any reason.

5.4.5 Device Malfunction or Failure

One device (Aerogen Pro-X controller, Aerogen Pharma Breath Controller, Flow Sensor, Solo nebulizer, CNTS syringe, and associated components) is expected to perform throughout the duration of study treatment. If the controllers, Flow Sensor, CNTS syringe, or the Solo nebulizer are not functioning optimally for any reason, instructions for trouble-shooting provided in the device instruction for use manual should be followed. If one or more devices need to be replaced, the reason should be documented in the patient's medical record, dispensing log, and Device Performance Issues Form. Additional devices are provided for this purpose. The unique serial numbers of the new components will be recorded in the patient's medical record, dispensing log, and the source documentation.

For device malfunction or complaints, complete the Device Performance Issues Log and submit to the Sponsor at [contact] within 48 hours. Failed devices will be set aside from the general supplies, inventoried and returned to the Sponsor or the Sponsor's designee.

5.5 Blinding

Since this is an open-label study, there will be no blinding of the study medication.

5.6 Prior and Concomitant Therapy

For patients who receive study medication, any medication (including over-the-counter [OTC] medications) or therapy administered to the patient during the course of the study (starting at Screening and 14 days prior) will be recorded on the Prior and Concomitant Therapy data collection forms. The Investigator will record any AE on the AE data collection forms for which a concomitant medication/therapy was administered.

5.6.1 Prohibited Concomitant Therapy

Other inhaled vasodilators besides VentaProst.

5.7 Investigational Product (IP) Supplies and Accountability

Investigational product supplies will not be sent to the Investigator(s) until the following documentation has been received by the Sponsor:

- Written proof of approval of the protocol and its informed consent forms (ICFs) by the Institutional Review Board (IRB)/Independent Ethics Committee (IEC) for the institution where the study is to be conducted.
- An Investigator-signed and dated FDA Form 1572.
- A signed and dated curriculum vitae of the Principal Investigator including a copy of the Principal Investigator's current medical license (required in the US) or medical registration number on curriculum vitae.

The Investigator and study staff will be responsible for the accountability of all IP supplies (dispensing, inventory, and record keeping) following Aerogen Pharma instructions and adhere to Good Clinical Practice (GCP) guidelines as well as local and/or regional requirements.

Under no circumstances will the Investigator allow the IP to be used other than as directed by this protocol. IP will not be administered to any individual who is not enrolled into the study.

An accurate and timely record of the receipt of all IP; dispensing of IP to the patient; collection of unused IP; and subsequent return of unused IP to Aerogen Pharma must be maintained. This includes, but may not be limited to: (a) documentation of receipt of IP, (b) IP dispensing log, (c) IP accountability log, (d) all shipping service receipts, and (e) documentation of returned IP to the Sponsor. All forms will be provided by Aerogen Pharma. Any comparable forms that the investigational site wishes to use must be approved by Aerogen Pharma.

The supplies and inventory records must be made available, upon request, for inspection by the designated representative of Aerogen Pharma, a representative of the FDA, or a representative of a non-US health authority. All used and unused IP are to be returned to Aerogen Pharma at the conclusion of the study.

6. CRITERIA FOR EVALUATION

6.1 Primary Endpoint

- 1. Reduction of respiratory failure. Failure is defined by any one of the following:
 - Requires VV ECMO
 - Inability to extubate within 10 days or reintubation within < 24 hours
 - Change in S/F, oxygenation index and P/F ratio (≥15%) from baseline to 12 hours, Days 1, 2, 3, 4, 5, 6, 7, 8, 9 and Day 10 (or end of treatment)

or

- 1. Reduction of cardiac or circulatory failure. Failure is defined by any one of the following:
 - Need to begin inotropic 10% increase in current vasopressor therapy
 - Worsening hemodynamic parameters

- Cardiac troponin >20% from baseline
- BNP > 15% of baseline
- Need for temporary mechanical circulatory support (IABP, Impella)
- Requires VA ECMO

6.2 Secondary Endpoints

- 1. Improvement in oxygenation defined as any one of the following:
 - Stabilization of PaO2/FIO2 >250
 - Improvement in FIO2 by 50% or improvements ≥15% in S/F, P/F ratio from baseline at 12 hours, Day 5 and Day 10 (or end of treatment)
- 2. Improved clinical outcomes defined as one of more of the following:
 - Time to extubation following the site's extubation protocol
 - Free from re-intubation
 - Reduction in ICU days
 - Reduction in the number of re-admissions to the ICU due to COVID-19 within 28 days
 - Reduction in total hospital days
 - Mortality [28 days] defined as Cardiopulmonary mortality from all causes
- 3. Safety and tolerability
 - Monitoring of adverse events (AEs), serious adverse events (SAEs), chest CT or Chest X-rays, vital signs, ventilatory/oxygenation parameters, and laboratory tests.

Exploratory endpoints will include (where available):

- Change in LDH
- Change in fibrinogen
- Change in WBC count including lymphocytes and neutrophil subsets
- Change in triglycerides
- Change in ferritin
- Change in CRP / ESR
- Change in IL-6
- Change in D-Dimer

6.4 Appropriateness of Measurements

All clinical assessments are standard measurements commonly used and generally recognized as reliable, accurate, and relevant in studies of cardiac and respiratory function.

7. SAFETY ASSESSMENTS

Safety will be assessed through monitoring of adverse events (AEs) and serious adverse events (SAEs), laboratory tests, chest assessments (Chest CT or Chest X-ray), oxygenation/ventilatory parameters, and vital signs. Safety assessment frequency is shown in the Schedule of Assessments and Procedures.

7.1 General Safety Procedures

7.1.1 Vital Signs and Weight Measurements

Vital sign measurements, including systolic blood pressure (SBP), diastolic blood pressure (DBP), heart rate (HR) [beats per minute], respiratory rate (breaths per minute), and body temperature (in Celsius) will be obtained twice daily Days 1-10 or as clinically indicated. Weight (kg) will be obtained at the time of Screening and at Day 10 or end of VP treatment. Height will be obtained at the time of Screening. If unable to obtain height, the study staff will use the best reported historical height from patient or LAR.

7.1.2 Physical Examination

A physical examination will be conducted at the screening visit and will include assessments of general appearance; skin and lymphatics; eyes, ears, nose, throat; cardiovascular system; respiratory system; abdomen/gastrointestinal system; urological system; musculoskeletal and neurological systems. Other body systems may be examined as clinically indicated.

7.1.3 Laboratory Measurements

Clinical laboratory measurements to be performed are listed below. The Schedule of Assessment				
and Procedures shows the time points at which blood will be collected for clinical laboratory tests				
pregnancy testing. The Baseline for laboratory tests is the Screening assessment.				
Category	Parameters			
	Hemoglobin, hematocrit, RBC, WBC with differential			
Hematology-CBC with diff	(neutrophils, lymphocytes, monocytes, eosinophils,			
	basophils), platelets			
Full Chemistry Panel				
Electrolytes	Sodium, potassium, chloride, bicarbonate, calcium			
Liver function tests	AST, ALT, AP, total bilirubin			
Renal function parameters	BUN, creatinine			
Coagulation Studies	PT/PTT, D-Dimer			
	Serum or urine pregnancy test, RT-PCR for COVID-19,			
Other	ESR, Troponin, BNP, fibrinogen, ferritin, LDH,			
	Triglycerides, D-Dimer, IL-6, and CRP			

7.1.4 Chest Assessments

A Chest CT or Chest X-ray will be obtained at Screening and Day 5.

7.1.5 Time Prone Protocol

The time prone protocol is a standard of care in OSU's ICU. This will be in place for all days that patients are within the ICU.

7.2 Adverse Events

7.2.1 Definitions

Adverse events are any untoward medical occurrence in a patient administered a pharmaceutical product and which does not necessarily have to have a causal relationship with this treatment. For the purposes of this study, this will include unanticipated medical events in the judgment of the investigator. *A pre-existing condition* or symptom is one that is present at the start of the study and is reported as part of the patient's medical history. A pre-existing condition or symptom should be reported as an AE only if its frequency, intensity or character worsens during study treatment.

All AEs that occur from the time of the first dose of study medication through the End of Study (Day 28) will be recorded and reported as Treatment-Emergent Adverse Events (TEAE). All AEs must be appropriately documented in the patient's medical chart/source documentation and on the DCFs. When known, investigators should report syndromes rather than list symptoms associated with the syndrome.

All AEs that are ongoing at the conclusion of the study should be followed until: a) resolution/stable sequelae; b) the Investigator determines that it is no longer clinically significant; or, c) the study patient is lost to follow-up. If no follow-up is provided, the Investigator must provide a written justification.

7.2.2 Grading of Adverse Events

The severity of each AE will be categorized using the following criteria:

- Grade 1 (Mild): usually transient; requires no special treatment and does not interfere with the patient's daily activities.
- Grade 2 (Moderate): produces a low level of inconvenience to the patient and may interfere with daily activities. These AEs are usually ameliorated by simple therapeutic measures.
- Grade 3 (Severe): interrupts daily activity and requires systemic drug therapy or other medical treatment.

7.2.3 Relationship to Study Medication/Study Device/Procedure

The Investigator must assess the relationship of each reported AE. The Investigator must make an assessment of the relationship of the AE to the study medication/study device/procedure using the following scale:

- Unrelated: The AE is definitely not or unlikely to be associated with study medication/study device/procedure and is judged due to causes other than the study medication/study device/procedure.
- Related: The AE is possibly or probably related with study medication/study device/procedure.

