2.2.4 Summary of Clinical Results

The safety and tolerability of VentaProst were evaluated in a Phase 2a Clinical Study in cardiac surgery patients "A Two-Part Pharmacodynamic Study to Compare VentaProstTM (Epoprostenol Solution for Inhalation via Custom Drug Delivery System) Dosing to Conventionally Administered Aerosolized Epoprostenol Dosing in Cardiac Surgery Patients" (NCT03122730).

Overall, 15 patients were exposed to doses of VP from 3.4 to 20.4 ng/kg/min in this study. Administration of VP in this dose range was well-tolerated. Overall, there were 2 patients (28.6%) in Part I and 1 patient (12.5%) in Part II who experienced a total of 7 TEAEs. All 7 TEAEs were assessed by the investigator as related to the surgical procedure and as unrelated to the study drug and unrelated to the device. No deaths occurred during the study. A total of 3 patients had 1 SAE each. All 3 SAEs were considered to be unrelated to the study drug or the study device.

Seven patients were evaluated in Part I to determine the effective dose equivalence between VP delivered at 17 ng/kg/min and off-label aerosolized Veletri administered at 50 ng/kg/min during mechanical ventilation. In all patients, VP 17 ng/kg/min was found to be equivalent either by calculation of effect compared with aerosolized Veletri 50 ng/kg/min or the investigators' judgement. In most patients, no differences were observed in oxygen saturation ranges between VP and aerosolized Veletri treatments at the same FiO2 while on the ventilator. The investigator determined that oxygenation, assessed by oxygen saturation measurements, did not change disproportionately with ventilator operating parameters on VP compared with aerosolized Veletri.

Eight patients were evaluated in Part II of the study to identify the optimal dose of VP. In the investigator's judgement, the optimal VP dose was determined to be 6.8 ng/kg/min in 2 patients, 10.2 ng/kg/min in 3 patients, and 13.6 ng/kg/min in 3 patients, which is the minimal dose that reliably produced a maximum hemodynamic response in all patients.

There have been no clinical trials to date with VentaProst in COVID-19 patients.

See IB for additional clinical information regarding inhaled epoprostenol.

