4.4.1 Criteria for Stopping VentaProst Treatment

Individual patients stopping criteria: At any time during study drug administration, patients may be removed from study treatment and placed on standard of care (SoC) therapy if they meet one or more of the following pre-defined criteria leading to a deterioration in their condition:

- Severe hypotension as evidenced by a systolic BP < 90 mmHg or MAP < 60 mmHG for >2 hours from the start of VentaProst
- Need for VV ECMO
- Need to increase existing vasopressor therapy by more than 25%
- Worsening oxygenation, ventilatory, or hemodynamic parameters that in the opinion of the investigator the patient should be removed from study treatment
- Massive hemoptysis thought to be clinically significant and not due to endotracheal tube trauma
- Pulmonary Edema

Study stopping criteria: If 3 patients are removed from the study for any of the above conditions, the study will stop further enrollment and investigation will be conducted to determine the cause of the events. An independent safety evaluation will also be conducted. If it is suspected that the investigational product has caused the events, the study will be terminated.

Independent Safety Evaluation: Independent safety evaluation will be conducted by a licensed physician who is not involved in the VentaProst COVID-19 clinical study or the sponsoring organization.

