5.4.1.1 VentaProst Aerosol Delivery to Ventilated Patients

The VentaProst delivery system (Figure 1) consists of reusable and single-patient use disposable elements:

- 1. Reusable multi-patient use components consist of two electronic controllers with power supplies, Aerogen Solo Nebulizer Cable, and Sensirion Flow Sensor Cable. When used together, they synchronize aerosol generation with the patient's inspiratory pattern through a single-patient use, disposable administration kit.
 - Aerogen Pro-X, is a commercially available device (K120939²) cleared for use to continuously operate the disposable Aerogen Solo nebulizer. (item #1 Figure 1).
 - Aerogen Pharma Controller (AP Controller) is an investigational device, which synchronizes aerosol generation with the ventilator inspiratory cycle (item #2 on Figure 1). This controller was tested to demonstrate its safety for use under IND129777.
 - Aerogen Solo Nebulizer Cable
 - Sensirion Flow Sensor Cable

2. Single-patient disposable kit:

- Aerogen Solo nebulizer (item #3 on Figure 1) is a commercially available, low mass and low profile vibrating mesh aerosol generator (K070642) cleared for use with the Aerogen Pro-X controller and Aerogen Continuous Nebulization Tube Set (CNTS).
- o Aerogen CNTS and syringe (items #4 and 5 on Figure 1) is a commercially available device (K103635) cleared for use to connect to the Aerogen Solo and deliver medication from the drug reservoir (syringe) to the mesh the nebulizer.
- Flow sensor and cable connected to the Aerogen Pharma Controller (AP Controller, item #7 on Figure 1). This is a new component of the system, which was tested to demonstrate safety for use in a clinical study.

The VentaProst delivery system will be used in conjunction with a commercially available and FDA-cleared syringe pump (item #8 on Figure 1). In general, any available syringe pump, which (1) is compatible with the Aerogen Continuous Nebulization Tube Set (CNTS syringe and tubing), and (2) is capable of delivering medication to the vibrating mesh nebulizer within the range of 0.4 to 12.0 mL/h as required to deliver the doses specified in the APC-VPCOV-CLN-001 Pharmacy Manual. For purposes of the VPCOV study, Aerogen Pharma will supply the Perfusor® Space Infusion Syringe Pump System from B.Braun (Figure 1). This particular syringe pump is FDA-cleared (K093913), it is compatible with the CNTS syringe (items #4 on Figure 1) and is able to

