7.2.4 Relationship to Study Medication/Study Device/Procedure

The Investigator must assess the relationship of each reported AE. The Investigator must make an assessment of the relationship of the AE to the study drug/study device/procedure using the following scale:

- Unrelated: The AE is definitely not or unlikely to be associated with study medication/study device/procedure and is judged due to causes other than the study medication/study device/procedure.
- Related: The AE is possibly or probably related with study medication/study device/procedure.

7.2.5 **AE Outcomes**

The following terms and definitions are used in assessing the final outcome of an AE:

- Recovered/Resolved The patient has fully recovered, or by medical or surgical treatment, the condition has returned to the level observed at the first trial-related activity.
- Recovering/Resolving The condition is improving and the patient is expected to recover from the event.
- Recovered/Resolved with sequelae The patient has recovered from the condition, but with lasting effect due to a disease, injury, treatment or procedure. If a sequela meets an SAE criterion, the AE must be reported as an SAE.
- Not recovered/Not resolved The condition of the patient has not improved and the symptoms are unchanged, or the outcome is not known at the time of reporting.
- Fatal This term is only applicable if the patient died from a condition related to the reported AE. Outcomes of other reported AEs in a patient before he/she died should be assessed as "recovered", "recovering", "recovered with sequelae" or "not recovered". An AE with fatal outcome must be reported as an SAE.

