7.2.8 Reporting for SAEs (24 Hours)

Regardless of causality, an SAE must be followed clinically until resolution or stabilization.

All SAEs after randomization and through Day 28 of the study must be reported to the Sponsor or the Sponsor's representative within 24 hours of the investigational site's knowledge of the occurrence. The investigational site will email a Serious Adverse Event Report (SAER) to the Sponsor and the Medical Monitor. Investigational sites will be provided with SAER forms. The Medical Monitor will work closely with the Sponsor to properly assess and report the SAE.

The SAE information emailed to the Sponsor or the Sponsor's representative will include the following (as available):

- Patient Number, Investigator name, and Site Number
- SAE information: event term, onset date, severity, and causal relationship
- Basic demographic information (e.g., age, gender, weight)
- The outcomes attributable to the event (death, a life-threatening adverse drug experience, inpatient hospitalization or prolongation of existing hospitalization, a persistent or significant disability/incapacity, other important medical event[s])
- A summary of relevant test results, pertinent laboratory data, and any other relevant medical history
- The first and last dates of study drug administration.
- A statement whether study medication was discontinued or study medication administration schedule modified
- A statement whether event recurred after reintroduction of study medication if administration had been discontinued or withheld
- Supplemental anonymized information may include the following hospital records: laboratory results, radiology reports, progress notes, admission and emergency room notes, holding/observation notes, discharge summaries, autopsy reports, and death certificates

Supplemental information may be transmitted using a follow-up report and should not delay the initial report.

For regulatory purposes, initial reports of SAEs should be transmitted within the prescribed time frame as long as the following minimum information is available: patient number, suspect study medication, reporting source, and an event or outcome that can be identified as being both serious and unexpected for which the Investigator can make a relationship assessment.

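### Section 7.2.4 rates drug, device and procedure on one combined causality scale, so as written a Related label cannot attribute an individual AE or SAE to the drug or to the investigational device

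*Combined protocol and SAP*

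**What the plan says.** The point concerns the current version, the latest of the double-blind, placebo-controlled protocols.

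- **Section 7.2.4, instruction:** "The Investigator must make an assessment of the relationship of the AE to the study drug/study device/procedure using the following scale". Two levels follow.
- **Section 7.2.4, Unrelated:** the event is definitely not, or unlikely to be, associated with the three items and "is judged due to causes other than the study medication/study device/procedure".
- **Section 7.2.4, Related:** "The AE is possibly or probably related with study medication/study device/procedure". The same sentence stood in section 7.2.3 of the superseded open-label version.
- **Section 7.2.8, SAE report:** one causality item, in the line "SAE information: event term, onset date, severity, and causal relationship".
- **Section 5.4.1.1:** "Aerogen Pharma Controller (AP Controller) is an investigational device", and the flow sensor is described as new to the system.
- **Sections 3.3 and 10.4:** Control is saline through the same delivery system, 10 patients per arm, randomised 1:1.
- **Section 10.8.1 and the synopsis (Safety Analyses):** AEs are summarised by incidence in both groups. No summary by relatedness is described.
- **Section 2.2.4:** in the sponsor's earlier cardiac-surgery study of VentaProst, the TEAEs were "assessed by the investigator as related to the surgical procedure and as unrelated to the study drug and unrelated to the device".

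**The concern.** VentaProst is a drug/device combination, and safety and tolerability belong to the secondary objective (section 3.2). A reader of an AE listing or an SAE report will want to know whether a Related event points to epoprostenol, to the aerosol system or to something done to the patient for the study. The scale does not ask for that.

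The plan relies on such distinctions elsewhere. Section 7.2.2 makes pulmonary hemorrhage an event of special interest because of how epoprostenol acts. Section 4.4.1 separates hemoptysis due to endotracheal tube trauma from other massive hemoptysis. At stake is the interpretation of single cases, above all SAEs, and the ability to recognise harm from an investigational device that every patient receives.

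**Working it through.** The documents contain no figure to reproduce on this point. The check has two parts: what the scale does to an event, and what the randomised comparison can recover.

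**1. The scale, read literally.** Unrelated requires a cause other than drug, device and procedure together. Related needs only a possible link.

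| Investigator's view of the cause | Meets Unrelated? | Label |
|---|---|---|
| Drug only | No | Related |
| Device only | No | Related |
| Procedure only | No | Related |
| COVID-19 or another cause only | Yes | Unrelated |

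Three yes/no attributions give 2 × 2 × 2 = 8 combinations. One (no, no, no) is Unrelated and the other 7 are Related. The label cannot be decoded afterwards. Because procedure is undefined, it is also unclear whether background ICU care counts. Section 2.2.5 mentions venipuncture as an example of a common procedure; sections 5.4.2 and 7.1.5 treat ventilation and proning as standard of care.

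**2. Device harm in the between-arm contrast.** Suppose, as a simple additive approximation, that the AE rate in Control is b + d (background plus device) and in Active b + d + g (plus the inhaled drug solution). The difference is (b + d + g) − (b + d) = g. The device term d drops out. The Device Performance Issues Log (section 5.4.5) records malfunctions and complaints, not AE causality, so it does not restore d.

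**3. Drug harm in the between-arm contrast.** Inputs: 10 per arm (section 3.3); two-sided Fisher exact test at 0.05 (my choice; the plan names no test for AEs); AE rates assumed, because the documents give none.

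Smallest detectable splits, with equal arms so that the two tails are symmetric:

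- 5/10 against 0/10: p = 2 × C(10,5) / C(20,5) = 2 × 252 / 15,504 = 0.033.
- 4/10 against 0/10: p = 2 × 210 / 4,845 = 0.087.
- 7/10 against 1/10: p = 2 × (1,200 + 45) / 125,970 = 0.020.
- 6/10 against 1/10: p = 2 × (2,100 + 120) / 77,520 = 0.057.

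So 5 of 10 in Active are needed when Control has none, and 7 of 10 when Control has one.

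Exact power is the sum, over all pairs of counts with p ≤ 0.05, of the two binomial probabilities multiplied together:

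| Assumed AE rate, Active | Assumed AE rate, Control | Power |
|---|---|---|
| 30% | 10% | 0.06 |
| 40% | 10% | 0.15 |
| 50% | 10% | 0.30 |
| 60% | 10% | 0.47 |

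The contrast exists, but it detects only very large differences. It compares epoprostenol in its diluent with saline, and it speaks for groups, not for single events.

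**The case against.** The strongest reply is that the slashes may be shorthand for three ratings. The AE data collection form is not among the documents, and section 2.2.4 shows the sponsor reporting the three components separately before. That stands as a possibility, so the finding is about the rating as written. It also shows that separate ratings are feasible and that the rule should be stated.

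The reply also limits several stronger readings that a reader might infer:

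- **That the trial cannot identify drug harm at all.** Not supported. Randomised saline through the same device gives a group-level contrast, though a weak one.
- **That a drug signal is diluted in the planned tables.** Not supported. Section 10.8.1 plans incidence, with no table by relatedness. The effect falls on case attribution and SAE reports.
- **That the termination decision in section 4.4.1 lacks evidence.** The rule reads "If it is suspected that the investigational product has caused the events, the study will be terminated", but the same section requires an investigation and an independent physician's evaluation, and section 5.5 allows unblinding. The investigational product includes both drug and device (sections 5.1 and 5.4), so that question does not need them separated; only the inclusion of procedure blurs it.
- **That the earlier study measures the mislabelling to expect here.** Its 3 affected patients of 15 had events tied to cardiac surgery, which is not part of this trial. The fraction does not transfer.
- **That Related events in Control must come from the device or a procedure.** Investigators are blinded, and study drug covers both arms, so they may rate a Control event as possibly drug-related.

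**Conclusion.** The concern holds in a limited form. As section 7.2.4 is written, the causality rating cannot attribute an individual AE or SAE to the drug or to the investigational device, and section 7.2.8 repeats the single item. Seven of eight attribution patterns share one label. Randomisation offsets this only in part: power is roughly 0.06 to 0.47 over the assumed rates for drug harm, and device harm common to both arms is invisible in the contrast.

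The conclusion rests on the literal reading of the slashes, which the unseen form could soften. The power figures rest on assumed AE rates and on Fisher's test. The frequency of device-only or procedure-only events cannot be estimated from the documents, so I give no expected count of mislabelled events. The change is worth making because it is cheap and case-level causality matters in a 20-patient study of a combination product. It does not put the planned incidence tables in doubt.

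**What to change.** - **Section 7.2.4:** require three separate Related/Unrelated ratings for every AE: study drug, study device (controllers, flow sensor, nebulizer, tubing and syringe) and study procedure. Define procedure as procedures done specifically for the study.
- **Section 7.2.8:** split the causality item in the SAE report in the same way.
- **Section 10.8.1:** tabulate drug-related and device-related AEs by arm.

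The cost is two more fields on the AE form (one rating becomes three), the same split on the SAE report and one more table. It needs no extra visits and no change to patient care. One limit remains: blinded investigators will still rate some Control events as drug-related, so the new table should be read by comparing arms and not as a count of true drug reactions.
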